4.3. Required Evaluations/Management (baseline prior to initiation of any protocol treatment)

- a) Cystoscopic evaluation by the participating urologic surgeon no more than 6 weeks prior to registration will include bimanual examination under anesthesia, as thorough as possible, a transurethral resection of the bladder tumor. Patients referred from an outside hospital with a muscularis propria-invading bladder tumor will be re-resected by the participating urologist.
- b) Radiologic evaluation including chest CT, abdominal and pelvic CT and bone scan no more than 6 weeks prior to start of treatment.
- c) Comprehensive metabolic panel (CMP) obtained no more than 4-6 weeks prior to registration

5. Randomization

5.1 Radical Cystectomy Arm- Those randomized to “Radical Cystectomy” will be scheduled for surgery. In brief, radical cystectomy is the removal of the entire bladder, nearby lymph nodes (lymphadenectomy), part of the urethra, and nearby organs that may contain cancer cells. In men the prostate, the seminal vesicles, and part of the vas deferens are also removed. In women the cervix, the uterus, the ovaries, the fallopian tubes, and part of the vagina are also removed. Participants in this group may also undergo neoadjuvant chemotherapy prior to the surgery as is the current standard of care. The decision for specific chemotherapy regimen is based on medical oncologist’s evaluation. All AE occurring during the study period will be assessed and attribution assigned.

The surgical approach, robotic versus open, is determined by patient and surgeon mutual preference. All urinary diversions will be done via an open incision and the mode of diversion, whether intracorporeal or extracorporeal (orthotopic neobladder, continent cutaneous diversion or ileal conduit) will be selected by mutual agreement of the surgeon and patient, as is customarily done. The extent of the lymph node dissection will be determined by the surgeon but at minimum will include the external iliac, obturator, and hypogastric regions.

Lymph node dissection: Minimum lymph node (men and women) – all potential lymph node bearing tissue with the lateral limit the genitofemoral nerve, distally Cooper’s ligament to include the lymph node of Cloquet, proximally the crossing of the ureter over the common iliac vessels, medially the bladder to include the tissue medial to the hypogastric artery, posteriorly the floor of the obturator fossa with circumferential mobilization of the external iliac artery and vein.

5.2 Chemoradiation Arm - Those randomized to chemoradiation will undergo radiation therapy concurrently with chemotherapy which serves as radiosensitizer. The following is a brief outline of the radiation therapy. Specific treatment frequency and dosage will be at the discretion of the treating physician/center.

Radiation Therapy (Protocol treatment must begin within 8 weeks following transurethral resection and endoscopic evaluation)

All patients who are randomized to bladder preservation arm will receive the induction course of chemoradiation first. This regimen will begin within 8 weeks following the TUR and cystoscopic evaluation by the participating urologic surgeon. Patients with a complete response to the induction regimen will receive consolidation chemoradiation, starting 7-14 days after cystoscopic re-evaluation. Ideally, treatment should begin on a Monday for both Induction and Consolidation chemoradiation.

5.2.1 Dose Specifications

a) Induction Treatment

On the induction regimen, radiation treatment is delivered one time per day (QD). For the first 10 treatment days, 2 Gy is delivered to the CTVpelvis. Then, 2 Gy is delivered to the CTVbladder for the next 4 treatment days, followed by 2 Gy to the CTVboost for the remaining 6 treatment days. This induction course will deliver a total of 40 Gy to the

CTVboost (20 Gy from the pelvic fields, 8 Gy from the bladder fields and 12 Gy from the tumor boost).

b) Consolidation Treatment

On the consolidation regimen, radiation treatment is delivered to the CTVpelvis at 2 Gy per fraction one time per day (QD) over 12 treatment days for a total of 24Gy. This is the same pelvic field that was treated as a component of induction therapy. For patients completing both induction and consolidation treatment, the resulting total dose to the CTVboost will be 64 Gy over 10 weeks in 32 fractions. The total dose to the CTVpelvis will be 44 Gy.

c) Radiation Dose Prescription

The dose should be prescribed at the center of each treatment volume (CTVpelvis, CTVbladder, CTVboost), or the mid-plane of the patient if only AP/PA beams are used. Criteria for dose coverage are specified in Section 4.6.3.

5.2.2 Technical Factors

The radiation treatment should be with a high energy linear accelerator with photon energies ≥ 6 MV.

5.2.3 Localization, Immobilization and Simulation

a) Immobilization

Proper immobilization is required for this protocol but the specific method of immobilization is up to the discretion of the treating institution. Patient setup reproducibility must be achieved using appropriate clinical devices that might include customized body fix and/or leg immobilizers.

b) Simulation

A planning CT must be obtained with the patient in the supine position. CT scan thickness should be ≤ 3 mm through the region that contains the target volumes and the critical structures requiring Dose-Volume histogram analysis. CT scan should extend at least 4cm above and below the target volumes. The superior limit of the scan will be at least at the L1/2 interspace and the inferior limit will be below the perineum.

The bladder must be voided prior to simulation. Use of IV, bladder or oral contrast is optional. Use of a urinary catheter at the time of simulation or cystoscopic placement of bladder fiducials prior to simulation is also optional. If bladder contrast is used, a 40-50 ml air contrast cystogram is recommended.

5.2.4 Treatment Planning/Target Volumes

a) Small Pelvic Fields

These fields should encompass the entire bladder (CTVbladder), the bladder tumor volume (CTVboost), prostate and prostatic urethra (in men), and the regional lymph nodes. These lymph nodes include the internal and external iliacs and the obturator lymph nodes. All of these structures constitute the CTVpelvis.

Four shaped anterior, posterior and lateral fields will be used. In the cranio-caudal dimension, these fields will extend from the lower pole of the obturator foramen to the mid-sacrum (the anterior aspect of S2-S3 junction). Laterally, the anterior-posterior opposed fields will extend 1.5 cm beyond the widest point of the bony margin of the pelvis. For the parallel opposed lateral fields, the anterior and posterior field edges will extend 2 cm beyond the CTVpelvis.

Field shaping will be used on the anterior-posterior opposed fields to shield the medial border of the femoral heads. Shaping will also be employed on the lateral opposed fields

inferiorly to shield soft tissue anterior to the pubic symphysis and to block the anal canal posteriorly. Superiorly, the lateral fields may include shaping anteriorly to exclude small bowel and anterior rectus fascia which lay anterior to the external iliac lymph node chain.

Wedges should be considered in the lateral fields as tissue compensators if there is a significant anterior slope. Weighting of the four field arrangement should be considered in light of the tumor boost planned such that the final dose to the femoral heads is no more than 45 Gy and the final dose to the posterior rectum is no more than 55 Gy.

Anatomic variations in the bladder may necessitate CTV pelvis modifications and deviation from the standard protocol defined field borders. Examples include a bladder cystocele protruding below the obturator foramen, a bladder diverticulum, bladder herniation through the abdominal wall, or a significant post-void residual. For any of these anatomic variations, the variation should be encompassed within the defined CTV bladder which in turn is used to define the CTV pelvis, and the field edge adjusted to extend 2 cm beyond the modified CTV pelvis.

b) Whole Bladder Fields

The CTVbladder includes the gross tumor volume (GTV) plus the whole bladder volume including the bladder wall thickness. This volume is covered using a four-field arrangement. Field edges extend 2 cm beyond the CTVbladder. Likewise, field shaping is employed to cover the CTVbladder with a 2 cm margin.

c) Tumor Boost Fields

The gross tumor volume (GTV=CTVboost) is derived from information available from bimanual examination, cystoscopic bladder mapping, intraoperative reports and radiographic studies. Close cooperation with the treating urologist is essential. Cystoscopically placed fiducial markers may be employed. A variety of field arrangements may be considered for treating this volume and efforts should be made to spare uninvolved regions of the bladder. Opposed lateral fields are frequently employed for posterior lesions. Well lateralized lesions may be amenable to an anterior-posterior field arrangement or a wedged pair. Regardless of the chosen field arrangement, the field edges should extend 2 cm beyond the defined GTV. The boost field arrangement needs to be determined early in the planning process as it may impact field weighting in the other phases of treatment such that final doses to the femoral heads and posterior rectum are within specified limits.

5.2.5 Critical Structures

The rectum volume is defined on CT from the anus (at the level of the ischial tuberosities) for a length of 15 cm or to the rectosigmoid flexure. A DVH for the rectum, bladder, and both femoral heads should be submitted. The following DVH criteria should be achieved.

Rectum:

No more than 50% of the volume above 30 Gy
No more than 10% of the volume above 55 Gy

Femoral heads:

No more than 20% of the volume above 50 Gy

5.2.6 Compliance Criteria

a) Field Borders

Variation: Actual field borders and/or PTVs are within 2 cm beyond those stated in the protocol and include the target structures described above.

Deviation: Actual field borders and/or PTVs transect a target structure or are greater than 2 cm beyond the borders stated in the protocol.

b) Specified Radiation Dose (Critical structures)

Variation: Planned dose is within 10% of the specified protocol dose.

Deviation: Planned dose deviates by more than 10% from the specified protocol dose.

c) Minimum Isodose Coverage (Applies to each CTV independently)

Generally the minimum dose to any target should be 95 % of the prescription dose to that target. To address the single pixel calculation anomalies the D99% is used as the dose specifier.

Per protocol: D99% > 95%. Dose covering 99% of the volume of any target volume is no less than 95% of the prescribed dose.

Variation: D99% < 95% but D99% > 90%. Dose covering 99% of the volume of any target

volume is no less than 90% of the prescribed dose.

Deviation: D99% < 90%. Target structures coverage falls below 90% of the prescribed dose.

d) Maximum Dose (Applies to each CTV independently)

Generally the maximum dose to any target should be less than 107% of that target's prescribed dose.

Per protocol: V107% < 0.12 cc. Less than 0.12 cc of the CTV receives a dose exceeding 107% of the prescribed dose.

Variation: V107% > 0.12 cc but this dose does not exceed 110% of this dose.

Deviation: The maximum dose to the 0.12 cc volume does exceed 110% of the prescribed dose.

e) Elapsed Days

Per protocol: No more than 3 break days

Variation: 4 to 7 break days

Deviation: 8 or more break days

5.2.7 Treatment Interruption (12/6/15)

If a grade 3 hematologic toxicity (ANC or platelets) develops during chemoradiotherapy, all treatment (both radiation and chemotherapy) should be discontinued for a minimum of 1 week.

Treatment may be resumed when the hematologic toxicity resolves to \leq grade 2. If these laboratory values have not been reached after a 1-week delay, they should be checked weekly until they become acceptable. If after 3 weeks the blood counts have not recovered, all protocol treatment should be discontinued and the patients should be treated on an individual basis.

For a grade 3 acute colitis, cystitis, or any other grade 3 infield (radiation-related) toxicity during any treatment week, treatment should be delayed until the toxicity subsides to the grade 2 level. If the delay is greater than 3 weeks, then the patient should be considered intolerant of protocol therapy and appropriate off-protocol therapy given.

5.2.8 Radiation Adverse Events

- *Genitourinary*: Frequency, nocturia, acute or chronic bleeding from the bladder mucosal surface, cystitis, ureteral obstruction, erectile dysfunction in men, sterility
- *Gastrointestinal*: Rectal irritation, bowel obstruction or bleeding, rectal ulcers, hematochezia, fistula formation, colitis, mucous-like stools
- *Dermatologic*: Erythema, loss of pubic hair which could be permanent
- *Gynecological*: Dyspareunia, ovarian failure and sterility
- *General*: Weight loss, fatigue

5.3 DRUG THERAPY

Medical Oncologist will determine the chemotherapy regimen concurrently used with radiation as a radiation sensitizer. The following is a list of chemotherapeutic drugs that could be used per NCCN guideline:

Cisplatin

Cisplatin and 5-FU

5-FU and Mitomycin

Cisplatin and Paclitaxel

Low dose gemcitabine

All AE occur during the study period will be assessed and attribution assigned.

6. Post-Induction Response Evaluation (for Chemoradiation Arm only)

Following the completion of induction chemoradiotherapy and the evaluation of response all patients must be re-registered via cystoscopy and biopsy. At this time, the response results (biopsy results and cytology results) and the second phase of the treatment (i.e. radical cystectomy for tumor response $T \geq 1$ or consolidation chemoradiotherapy for tumor response T0, Ta, and Tcis) will be recorded and a new data collection calendar generated. Details regarding “Radical Cystectomy” can be found at Section 5.1. Details regarding “Consolidation Chemoradiotherapy” can be found at Section 5.2.2.

The following information will be supplied:

- original case number
- results of evaluation and pathologic T stage
- treatment start date (radical cystectomy or consolidation chemoradiotherapy)

The treatment option registered and the new data collection calendar will be based on the parameters specified by the protocol. If the investigator or the patient deviates from the protocol specified treatment, documentation of this and data submission as outlined in our study Standard operating procedure.

Patients who have developed distant metastases during the induction phase of treatment and who will not continue therapy will remain on the original calendar schedule for continued follow up only.

After completing either radical cystectomy or consolidation chemoradiotherapy, all response results to the second phase of treatment (i.e., either pathologic staging from the radical cystectomy or cystoscopic re-evaluation performed following completion of consolidation chemoradiotherapy) will be promptly submitted to Data Management.

7. 1 Post-Treatment Study Visits at 3, 6, 9, 12, 18, 24, 30, and 36 month \pm 1 month

Post-treatment study visits will occur every three months (\pm 1 month) up to one year and every six months (\pm 1 month) thereafter up to two years (i.e. Months 18, 24, 30, and 36). These study visits will be scheduled during the same time as the participant's routine visit (i.e. standard of care) whenever possible. If not, study team member will work with participant on a time that is convenient. An imaging study either a CT abdomen and pelvis or MRI of abdomen and pelvis will be done as standard of care prior to the routine clinic visit. The treating physician will assess AE and assign attribution. Research study team member will coordinate with the participant to meet either before or after the routine clinic visit. Participants will be asked to complete study questionnaires. The questionnaires may also be mailed and/or emailed back to the study team if they cannot be completed within the allotted study time. And those randomized to "chemoradiation Group" will also undergo routine cystoscopy during these follow-up visits (SOC).

7.2 Withdraw Visit

Whenever possible, participant will be scheduled for a withdraw visit if she/he chooses to withdraw from the study early or if the PI needs to withdraw the participant from the study. This is an optional visit. During this visit, participant will be asked to have research blood draw and complete study questionnaires. Reasons for withdraw will also be asked and recorded. Participant will have the choice to partake any or all of the activities during withdraw visit.

7.3 Unscheduled Visit

Date and reason for any study-related unscheduled visit will be recorded. Any medical notes, radiographic, and/or lab results related to this study-related unscheduled visit will also be obtained and recorded.

8. STUDY CALENDAR

8.1 RADICAL CYSTECTOMY ARM

	Initial visit	Pre-Treatment (tx) TURBT	Baseline	Treatment Period: Radical Cystectomy	Post-tx 3 mon f/u ± 1 mon	Post-tx 6 mon f/u ± 1 mon	Post-tx 9 mon f/u ± 1 mon	Post-tx 12 mon f/u ± 1 mon	Post-tx 18 mon f/u ± 1 mon	Post-tx 24 mon f/u ± 1 mon	Post-tx 30 mon f/u ± 1 mon	Post-tx 36 mon f/u ± 1 mon (end of study visit)		
Study eligibility	X		X											
Informed consent	X													
Assessment of AE						X	X	X	X	X	X	X	X	X
SOC Image studies (X-Ray, CT, and/or MRI)			X			X	X	X	X	X	X	X	X	X
Research blood sample			X			X	X	X	X	X	X	X	X	X
Ht, Wt, and Vitals [#]			X			X	X	X	X	X	X	X	X	X
Research Study Questionnaires			X			X	X	X	X	X*	X*	X*	X*	X*

Note:

SOC = Standard of Care

[#] information may be extracted from EMR

*Research study questionnaire may be emailed or mailed per patient's stated preference

8.2 CHEMORADIATION ARM

	Initial Visit	Pre-Treatment (tx) TURBT	Baseline	Treatment Period: Chemoradiation	Post-Induction Response Evaluation with Cystoscopy and biopsy (3-4 weeks following Induction Chemoradiotherapy) and second phase of treatment**	Post-tx 3 mon f/u ± 1 mon	Post-tx 6 mon f/u ± 1 mon	Post-tx 9 mon f/u ± 1 mon	Post-tx 12 mon f/u ± 1 mon	Post-tx 18 mon f/u ± 1 mon	Post-tx 24 mon f/u ± 1 mon	Post-tx 30 mon f/u ± 1 mon	Post-tx 36 mon f/u ± 1 mon (end of study visit??)			
Study eligibility	X		X													
Informed consent	X															
Assessment of AE								X	X	X	X	X	X	X	X	X
SOC Image studies (X-Ray, CT, and/or MRI)			X					X	X	X	X	X	X	X	X	X
Radiation & Medical Oncology Consults (SOC)			X													
Research blood sample			X					X	X	X	X	X	X	X	X	X
Ht, Wt, and Vitals [#]			X					X	X	X	X	X	X	X	X	X
Research Study Questionnaires			X					X	X	X	X	X*	X*	X*	X*	X*

Note:

SOC = Standard of Care

information may be extracted from EMR

*Research study questionnaire may be emailed or mailed per patient's stated preference

** Post-treatment cystoscopy is SOC for chemoradiation patients ONLY

**Pending on the results of post-induction TURBT and response evaluation, participant may receive further treatments. Details on the second phase of treatment are listed in Section 6 and Study Synopsis.

9. DATA COLLECTION & STUDY EVALUATIONS

Medical records will be reviewed prior to “Baseline Study Visit” to confirm study eligibility. After obtaining consent, socio-demographic data will be collected through chart review and interviews. Clinical data that will be collected include but not limited to bladder cancer treatment history, tumor characteristics, stage, laboratory results, medications and co-morbidity.

Study team member or clinic staff will measure height, weight, and vital signs at each specific study time point. Research blood will be drawn at each study time point. Blood and tissue samples may be banked under the optional study (HSC20050234H GU Tissue Bank). For those participants who declined to participate in the optional study, any leftover samples will be permanently de-identified through the GU Tissue Bank (HSC20050234H) honest broker system. At the close of this study, all biological materials collected will be rolled into HSC20050234 GU Tissue Bank.

9.1 Feasibility: We will report recruitment, visit dates, adherence, attrition rates and compliance with randomization for each arm of the study

9.2 Bladder-intact survival: We will report proportion of patients who failed chemoradiation and required salvage cystectomy

9.3 Quality of life: A self-assessment questionnaire using the European Organization for Research and Treatment of Cancer (EORTC) QLQ- C30 and FACT-Bladder will be used for QOL assessment at baseline, 3, 6, 9 and 12 months.⁸

9.4 Progression free survival: This will be measured from the date of finishing chemoradiation or radical cystectomy to the date of first documentation of progression. Progression will be determined using RECIST 1.1 criteria by the treating physician based on radiographic or pathologic evidence of disease progression, or death from disease. Any documented recurrence will be considered progression.⁹ The date of progression will be recorded.

9.5 Candidate gene expression analysis: For the participants who have consented to be part of the optional study (“GU Tissue Bank HSC20050234H), a microarray analysis will be performed on all bladder tumor specimens using Agilent Technologies (Agilent SurePrint G3 Human Gene Expression 8x60K v2) Microarray. Goal is to study the landscape of 50 important candidate genes, which are involved in bladder cancer (for example-BRAF, KRAS, EGFR, FGFR).

9.6 Activities of Daily Living (ADL) scores: This will be measured at baseline, and during all subsequent follow-up visit (i.e. 3, 6, 9 And 12 months) using Activities of Daily Living QOL Questionnaire using Katz Index of Independence in Activities of Daily Living (ADL).¹⁰

9.7 Retrospective screening & chart review: We will screen and review charts of “potential participant” retrospectively using the latest approved eligibility criteria and study schema to determine:

1. the number of “would-be potential participants”
2. the number of those who were initially deemed eligible and was truly eligible after TURBT
3. the number of those who were initially deemed eligible but was ultimately ineligible after TURBT

4. rationale for ineligibility

The retrospective screen & chart review will start from the date when the study was first approved by the IRB (i.e. April 15, 2016) until present time. Data including but not limited to medical record number, initials of name, gender, race, ethnicity, TURBT result, age at time of treatment, treatment received, date of treatment, eligibility status for the study, and rationale if deemed ineligible, will be captured. We do not intend to contact these patients for study enrollment since they would've received treatments for their diagnosis already. Our intention for this retrospective data collection is that it will provide further insight and information on the potentiality of chemoradiation as treatment modality for patients with specific bladder cancer diagnosis. We need to capture this data in order to represent total population of patients screened, thereby determining the denominator of the study population.

9. 8 Outline of Captured Data

Outcome of Interest	Measure	Method of Assessment
Demographics		Self-report questionnaire
Health History including height, weight, and vital signs		Physical exam, review of EPIC
Study Processes		
recruitment rate adherence attrition feasibility bladder intact survival safety		
Outcomes of interest		
Quality of Life	EORTC	Self-report questionnaire
	FACT-BI	Self-report questionnaire
ADL	Katz ADL	Self-report questionnaire
Progression free survival	RECIST 1.1	Physician assessment
Candidate gene expression	Candidate genes	Laboratory analysis of blood and tissue

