Categorical outcomes will be summarized with frequencies and percentages. Continuously distributed outcomes will be summarized with the sample size, mean, standard deviation, median, minimum and maximum. A consort diagram giving the number patients screened, the number of screen failures, the number randomized, the number lost to follow-up by reason, and the number completing the study by treatment arm will be created. In Aim 1a we will test the hypothesis that chemoradiation therapy is non-inferior to radical cystectomy with regard to change in quality of life at 36 months relative to baseline. In Aim 1b, we will test the hypothesis that chemoradiation is non-inferior to radical cystectomy with regard progression free survival and bladder intact survival. With regard to Aim 1a, assuming the 50% (p_2) of patients randomized to radical cystectomy and 60% (p_1) of patients randomized to chemoradiation will experience improvement in quality of life at 3 years relative to baseline and a 5% margin (Δ) of non-inferiority, this study would require $n=171$ subjects per group to attain 80% power for testing $H_0: p_1 - p_2 \leq \Delta$ versus $H_1: p_1 - p_2 > \Delta$ with $\alpha=5\%$. The non-inferiority of chemoradiation compared with radical cystectomy with regard to changes in quality of life (Aim 1a) will be assessed with Fisher's exact test. Progression free and bladder-intact survival (Aim 1b) will be summarized by treatment arm with Kaplan-Meier curves and supporting tabulations and non-inferiority will be assessed with a logrank test. The significance of treatment arm differences with regard to biomarkers (Aim 2a) will be assessed with t-tests or Wilcoxon tests. Pairwise correlations between biomarkers will be displayed overall and by treatment arm. Logistic regression will be used to find a best linear predictor of treatment arm in terms of multiple biomarkers. Biomarkers may be log transformed prior to analysis. Feasibility (Aim 2b) will be assessed with a new power and sample size calculation. If the logistic regression model fails in Aim 2a, random forests will be attempted. If the logrank test fails in Aim 1b, Fisher's exact test will be used. R (v3+, Vienna, Austria) or SAS (SAS Institute, Cary, North Carolina) software will be used throughout.

REFERENCES

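### Section 9.3 stops quality-of-life collection at month 12, but Section 11 tests Aim 1a on the change at month 36

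*Combined protocol and SAP*

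**What the plan says.** Four parts of the combined protocol and SAP bear on when quality of life is measured.

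- **Section 9.3 (Quality of life)** names the instruments, EORTC QLQ-C30 and FACT-Bladder, and says they "will be used for QOL assessment at baseline, 3, 6, 9 and 12 months". Section 9.6 gives the Katz ADL the same span: baseline and "during all subsequent follow-up visit (i.e. 3, 6, 9 And 12 months").
- **Section 11 (Statistical Considerations)** states the Aim 1a hypothesis as chemoradiation being "non-inferior to radical cystectomy with regard to change in quality of life at 36 months relative to baseline". Its sample-size assumption is the proportion in each arm who "will experience improvement in quality of life at 3 years relative to baseline".
- **Section 7.1** is headed "Post-Treatment Study Visits at 3, 6, 9, 12, 18, 24, 30, and 36 month" and says of these visits: "Participants will be asked to complete study questionnaires". It sets no 12-month limit and names no instrument.
- **Sections 8.1 and 8.2 (calendars)** each have a row labelled "Research Study Questionnaires" that is marked through to the final visits. An asterisk on the later marks allows return by mail or email. Again no instrument is named.

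**The concern.** The section that defines how quality of life is measured ends two years before the time at which it is to be analysed. Staff who take 9.3 as the rule for the QLQ-C30 and FACT-Bladder would stop both at month 12 and could point to the protocol for doing so. Staff who work from the calendar would continue to month 36.

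The stakes are higher than for most scheduling conflicts, for three reasons.

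- Quality of life is Aim 1a and the only outcome for which Section 11 gives a sample-size calculation.
- A patient-reported score that was not taken at the time cannot be reconstructed from the medical record.
- Section 11 gives no method for missing quality-of-life data, so there is no planned way to handle the gap.

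**Working it through.** **The plan's own figure.** Section 11 gives p1 = 0.60 (chemoradiation), p2 = 0.50 (cystectomy), margin 0.05, 80% power and alpha 5%, with 171 per group. With unpooled variance, the null at a difference of minus 0.05, and one-sided alpha 0.025:

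n = (1.960 + 0.842)² × (0.60 × 0.40 + 0.50 × 0.50) / (0.10 + 0.05)² = 7.849 × 0.49 / 0.0225 = 170.9, rounded up to 171.

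The stated figure reproduces. One-sided alpha 0.05 gives 135 and does not. The inputs are 3-year proportions, so the calculation rests on a month-36 measurement. Aligning the collection schedule changes none of these inputs. The sidedness of alpha and the sign of the margin in the printed hypothesis are separate matters.

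**The schedules side by side.**

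| Source | Post-baseline times | Instruments named for follow-up |
|---|---|---|
| Section 9.3 | 3, 6, 9, 12 | QLQ-C30, FACT-Bladder |
| Section 9.6 | 3, 6, 9, 12, described as all follow-up visits | Katz ADL |
| Section 7.1 | 3, 6, 9, 12, 18, 24, 30, 36 | None |
| Sections 8.1, 8.2 | To month 36 | None |
| Section 11 (analysis) | 36 | None |

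Section 4.2 names the QLQ-C30 and FACT-Bl as examples of the questionnaire packet, but for the baseline visit. Section 9.3 is therefore the only text that ties these two instruments to follow-up months.

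**Size if 9.3 is followed.**

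- Post-baseline assessments planned elsewhere: 8. Listed in 9.3: 4. Lost: 8 − 4 = 4 (months 18, 24, 30 and 36).
- Gap between the last score and the analysis time: 36 − 12 = 24 months.
- Patients with a month-36 score: 0 of 15 + 15 = 30.

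**Size if practice is mixed.** Each patient without a month-36 score is 1/15 = 6.7 percentage points of an arm. This is only the weight of one patient. It does not forecast how many would be missed, and the documents give no basis for such a forecast.

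**Whether the document settles the conflict elsewhere.** It does not. Section 7.1 describes visits after the first year as running for two years, yet lists months up to 36. The header of the last column in the Section 8.2 calendar still carries a query about whether it is the end-of-study visit. Section 10.2 ends adverse event documentation 30 days after the 12-month visit, although both calendars mark adverse event assessment beyond it. This pattern would fit text left over from a 12-month design, but that is inference and the conclusion does not depend on it.

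**The case against.** The strongest reply is that month-36 collection is planned. Section 7.1 asks for questionnaires at visits up to month 36, both calendars mark them, the mail-or-email footnote provides for the later ones, and Section 11 names 36 months or 3 years twice. Section 9.8 lists only the EORTC and FACT-Bl questionnaires and the Katz ADL as self-report outcome measures, so it is natural to read the unnamed study questionnaires as these. Section 9.3 does not say that later assessments are excluded. On this reading the intention is visible, 9.3 was simply not updated, and 0 of 30 is the worst case rather than the expected one.

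Much of this stands. The intended schedule probably is the 36-month one, and 0 of 30 holds only if 9.3 governs. But a probable intention is not an instruction. The one passage that gives follow-up times for the named instruments says 12 months, and it would have to be disregarded for the Section 11 analysis to be possible.

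A second reply is that this is a pilot. With 15 per arm against the 171 calculated, the month-36 test cannot be confirmatory whatever is collected. That is true of the test. It does not make the data dispensable. Section 11 says feasibility under Aim 2b will be judged by a new power and sample-size calculation, and the only such calculation in the plan uses 3-year quality of life. Without month-36 scores the pilot cannot revise the 50% and 60% assumptions, nor show that 36-month questionnaires can be obtained.

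**Conclusion.** The concern holds. Sections 9.3 and 9.6 conflict with Sections 7.1, 8.1, 8.2 and 11, and 9.3 is wrong as written: following it leaves the Aim 1a endpoint uncollected. The size is conditional. If 9.3 governs, all 30 patients lack a month-36 score. If the calendars govern throughout, none is lost for this reason. If practice is mixed, the loss lies between these. The conclusion assumes only that Section 11 states the intended analysis time. It should be corrected before patients pass month 12, because the loss cannot be reversed and the remedy is small.

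**What to change.** Amend Section 9.3 so that the QLQ-C30 and FACT-Bladder are given at baseline and months 3, 6, 9, 12, 18, 24, 30 and 36. Give the Katz ADL in Section 9.6 the same list. Both then match the visit months in Sections 7.1, 8.1 and 8.2 and the analysis time in Section 11, and each named instrument is tied to each visit.

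Two small edits are worth making in the same amendment: name the instruments in the questionnaire row of both calendars, and clear the two-year wording in Section 7.1 and the open query in the Section 8.2 header.

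The cost is protocol wording. No visit is added, the calendars already schedule the questionnaires with return by mail or email for the later ones, and the 171 per group is unaffected.
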